# 5.5. Multiplicity Strategy

No multiplicity adjustment needs to be considered for the effectiveness endpoints since no formal hypothesis testing will be conducted.

# 5.6. Subgroup Analysis and Effect of Baseline Factors

No subgroup analyses are currently planned.

# 5.7. Interim Analysis for Efficacy

No interim analyses for effectiveness endpoints are currently planned.

## 6. Safety Analysis Strategy

The focus of the safety analysis will be a comprehensive descriptive assessment of occurrence of AE as well as the other listed parameters. Therefore, no inferential testing will be done for the safety analysis.

# 6.1. Safety Endpoints

The safety endpoints for this study are:

- Biomicroscopy findings (including corneal staining)
- BCVA
- AEs
- Device deficiencies

# **6.2.** Safety Hypotheses

No inferences are to be made on the safety endpoints; therefore, no hypotheses are formulated.

# 6.3. Statistical Methods for Safety Analyses

The FAS will be used for all safety analyses. All safety endpoints will be summarized descriptively overall and by DED groups.

#### 6.3.1. Adverse Events

The applicable definition of an AE is in the study protocol. All AEs will be collected from the time of signed IC until study participation is complete. AEs will be coded using the most current available version of the Medical Dictionary for Regulatory Activities (MedDRA) at the time of the data-cut.

All analyses described will be based on treatment-emergent adverse events (TEAEs), if not otherwise specified. TEAEs are those events with onset dates occurring on or after the first dose of study treatment until the end of the study. AEs with an onset date missing will be considered as TEAE.

- **AEs related with study device**: AEs recorded on the AE eCRF page, Relationship to Study Device = Related) and those of unknown relationship (i.e., no answer to the question "Relationship to Study Device").
- **AEs related with test procedure**: AEs recorded on the AE eCRF page, Relationship to Test Procedure = Related) and those of unknown relationship (i.e., no answer to the question "Relationship to Test Procedure").
- Serious adverse events (SAEs): AEs recorded on the AE eCRF page, Was this a Serious Adverse Event? = Yes.
- AEs resulting in study device permanent discontinuation: AEs recorded on the AE
  eCRF page, Action Taken Due To Adverse Event = Study Device Permanently
  Discontinued.
- AEs resulting in death: AEs recorded on the AE eCRF page, Death = Yes or Outcome
   = Fatal.
- Ocular AEs: AEs recorded on the AE eCRF page, Eye = OD or OS.

TEAEs will be summarized as the number and percentage of subjects/eyes by MedDRA Preferred Terms (PT) as an event category. Each subject/eye will be counted only once within a given PT. TEAEs will be displayed in terms of frequency tables sorted on decreasing frequency of PT. In case of equal frequency regarding PT, alphabetical order will be used. In

case any specific TEAE does not have MedDRA PT coded term, it will be summarized under the "Uncoded" category.

The following tables will be created for non-ocular TEAEs (subject-level summary):

- The overall summary table of non-ocular TEAEs will include the number of non-ocular TEAEs and the frequency (number and percentage), and the corresponding 95% CI of subjects with:
  - o Any non-ocular TEAE
  - Any moderate non-ocular TEAE
  - o Any severe non-ocular TEAE
  - Any non-ocular TEAE related with study device
  - Any non-ocular TEAE related with test procedure
  - Any serious non-ocular TEAE
  - O Any serious non-ocular TEAE related with study device
  - o Any serious non-ocular TEAE related with test procedure
  - o Any non-ocular TEAE resulting in study device permanent discontinuation
  - o Any non-ocular TEAE resulting in death
- Non-ocular TEAEs by PT
- Serious non-ocular TEAEs by PT
- Non-ocular TEAEs related with study device by PT

For ocular TEAEs, the following data will be summarized (eye-level summary):

- The overall summary table of ocular TEAEs will include the number of ocular TEAEs and the frequency (number and percentage), and the corresponding 95% CI of eyes with:
  - Any ocular TEAE
  - Any moderate ocular TEAE
  - o Any severe ocular TEAE
  - o Any ocular TEAE related with study device
  - Any ocular TEAE related with test procedure
  - o Any serious ocular TEAE
  - o Any serious ocular TEAE related with study device
  - o Any serious ocular TEAE related with test procedure

- o Any ocular TEAE resulting in study device permanent discontinuation
- o Any ocular TEAE resulting in death
- Ocular TEAEs by PT
- Serious ocular TEAEs by PT
- Ocular TEAEs related with study device by PT

Supportive listings will be provided for all TEAEs. Ocular TEAEs will be flagged.

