# 1.3. Study Descriptions

#### 1.3.1. Overview of Study Design

This is a post-market, multicenter, non-comparative, single arm, open-label, prospective clinical study to assess the performance and safety of Systane Complete PF Lubricant Eye Drops in adult subjects experiencing DES.

The study will be conducted outside the US, where the product is commercially available, in clinical sites known to routinely manage subjects with DED.

[figure not shown]
Figure 1: Overall Study Design.

Systane Complete PF will be dispensed at Screening/Baseline visit. Subjects will be expected to attend one additional visit at Day 30 (±2days) after screening and a telephone call visit at Day 15 (±2days).

Eligible subjects will initiate treatment with Systane Complete PF. On Day 1, eligible subjects will be asked to instill one drop of Systane Complete PF in each eye on-site (during the Screening/Baseline visit) and the subsequent drop only after 8 hours (± 1 hour) at home. For the rest of the study duration (up to Visit 3), subjects will be asked to self-administer 1-2 drops in each eye; four times a day. The dose selected in this study is the dose approved for Systane Complete PF for the management of DED (Figure 2).

Figure 2: Systane Complete PF Dose Regimen.

As shown in Figure 1, subjects will participate in the study for approximately 30 days, with a phone call scheduled on Day  $15 \pm 2$  (Visit 2) and a follow-up visit scheduled on Day  $30 \pm 2$  (Visit 3). Subjects may have unscheduled visits if deemed necessary per the Investigator's judgment.

Subjects will be asked to complete subject questionnaires on Day 1 (Impact of Dry Eye on Everyday Life - Symptom Bother [IDEEL-SB] and at Visit 3 (IDEEL-SB). In addition, subjects will be instructed to document Systane Complete PF dosing information on a daily basis using a subject diary.

The overall study duration (first subject screened to last subject's final study visit) is expected to be approximately 2 months.

The schedule of study assessments is presented in Table 1.

Table 1: Data Collection Schedule

Procedure/Assessment	Visit 1 Screening/ Baseline (Day 1)	Visit 2 (phone) 15-day Follow-up (±2 days)	Visit 3 30-day / Exit (±2 days)	Unscheduled Visit / Early Exit
Informed consent (IC)	X			
Demographics	X	]		
Targeted medical history	X			
Targeted concomitant medications	X			
IDEEL-SB questionnaire	X		X	(X)
Inclusion/Exclusion	X			
Changes in concomitant medications		X	X	X

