# 3. General Aspects for Statistical Analysis

#### 3.1. General Methods

In general, summaries will present data overall and by DED groups (aqueous deficient DE, evaporative DE, and mixed DE).

No hypothesis testing will be performed. Whenever applicable, 95% confidence intervals (CIs) will be provided. For proportions, 95% CIs will be calculated using the exact Binomial (Clopper-Pearson) method [1]. 95% CIs of a normal distribution for means will be provided, as needed.

All relevant subject data will be included in listings. The listings will be sorted by subject ID, and other characteristics (age, sex, eye(s), etc.), if necessary.

Data collected for IDEEL-SB, BCVA, and Biomicroscopy findings at unscheduled visits may be included in by-visit summaries and analyzed in the same fashion as the data collected at scheduled visits except where otherwise noted.

SAS® version 9.4 or higher will be used for all statistical analyses and tabulations.

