#### 6.3.2. BCVA

BCVA will be assessed per standard practice at the Screening/Baseline visit (Day 1) and at Visit 3 (and at unscheduled and early exit visits, as necessary).

For each eye, the distance visual acuity (VA) will be collected as per the site's standard of care practice using charts validated for the specific testing distance, which may include for example, 6 m for Snellen chart, 20 ft for Snellen chart, decimal chart and logMAR score. The values for BCVA will be presented in logMAR. BCVA will be summarized as a continuous variable at each analysis visit (Baseline and Visit 3) [eye-level summary]. The mean BCVA score will be presented together with the corresponding 95% CI. In addition, the change from Baseline will be summarized at Visit 3.

A supportive listing for BCVA assessments will be provided.

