## 8. Sample Size and Power Calculations

The study will recruit 68 subjects with a target to complete 54 evaluable subjects.

With a sample size of 54, a two-sided 95% CI for a single proportion will extend 0.060 from the observed proportion when the expected proportion is 0.0543 (AEs). Table 3 presents the precision for various rates of categorical outcomes.

Table 3: Precision for Various Percentages

Sample Size	Pro	ecision (%) for V	arious Rates of Outo		
Sample Size	5%	10%	25%	50%	
54	5.81%	8.00%	11.55%	13.34%	

Precision calculated according to a simple asymptotic formula for a 2-sided 95% CI for a proportion based on the normal approximation of the binomial distribution.

Investigators will be asked to enroll approximately 22% of subjects with aqueous deficient DE, 45% of subjects with evaporative DE, and 33% of subjects with mixed DE as per the Tear Film and Ocular Surface Society (TFOS) Dry Eye Workshop (DEWS) criteria.

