## 13. Tables, Listings, and Figures

A separate document contains the shells to be employed in this study.

- Table 14.1.1.1: Subject Disposition
- Table 14.1.1.1.2: Subject Disposition by Site
- Table 14.1.2.1.1: Major Protocol Deviations FAS
- Table 14.1.3.1.1: Summary of Demographics and Baseline Clinical Characteristics FAS
- Table 14.1.3.1.2: Summary of Demographics and Baseline Clinical Characteristics by Site FAS
- Table 14.1.4.1: Summary of Treatment Duration and Missed Doses FAS
- Table 14.2.1.1.1: Summary of IDEEL-SB Score by Analysis Visit FAS
- Table 14.2.1.1.1.2: Summary of IDEEL-SB Score by Analysis Visit PP

- Table 14.3.1.1: Overall Summary of Non-Ocular Treatment-Emergent Adverse Events (TEAEs) FAS
- Table 14.3.1.2.1: Summary of Non-Ocular Treatment-Emergent Adverse Events (TEAEs) by MedDRA PT- FAS
- Table 14.3.1.2.2: Summary of Serious Non-Ocular Treatment-Emergent Adverse Events (TEAEs) by MedDRA PT FAS
- Table 14.3.1.2.3: Summary of Non-Ocular Treatment-Emergent Adverse Events (TEAEs) Related with Study Device by MedDRA PT FAS
- Table 14.3.1.3: Overall Summary of Ocular Treatment-Emergent Adverse Events (TEAEs) FAS
- Table 14.3.1.4.1: Summary of Ocular Treatment-Emergent Adverse Events (TEAEs) by MedDRA PT FAS
- Table 14.3.1.4.2: Summary of Serious Ocular Treatment-Emergent Adverse Events (TEAEs) by MedDRA PT FAS
- Table 14.3.1.4.3: Summary of Ocular Treatment-Emergent Adverse Events (TEAEs) Related with Study Device by MedDRA PT FAS
- Table 14.3.2.1: Summary of BCVA Score (logMAR) by Analysis Visit FAS
- Table 14.3.3.1: Summary of Biomicroscopy Findings by Analysis Visit FAS

- Table 14.3.3.2: Shift from Baseline to Visit 3 Biomicroscopy Findings FAS
- Table 14.3.3.3: Summary of Corneal Staining by Analysis Visit FAS
- Table 14.3.3.4: Shift from Baseline to Visit 3 Corneal Staining FAS
- Table 14.3.4.1: Summary of Device Deficiencies FAS
- Listing 16.2.1.1: Listing of Subject Disposition
- Listing 16.2.1.2: Listing of Missed Visits FAS
- Listing 16.2.2.1: Listing of Protocol Deviations FAS
- Listing 16.2.3.1: Listing of Demographics and Baseline Clinical Characteristics FAS
- Listing 16.2.3.2: Listing of Medical History and Concomitant Medication FAS
- Listing 16.2.4.1: Listing of Missed Doses FAS
- Listing 16.2.4.1: Listing of IDEEL-SB Questionnaire FAS
- Listing 16.2.5.1: Listing of Treatment-Emergent Adverse Events (TEAEs) FAS
- Listing 16.2.6.1.1: Listing of BCVA Assessments FAS

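### The study is sized on an AE proportion in subjects, but the SAP plans no subject-level rate for ocular TEAEs or any TEAE, and its eye-level 95% CIs ignore pairing of eyes

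*SAP*

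**What the plan says.** - SAP 8 (and Protocol 6.4.1) justifies the sample size by precision: "With a sample size of 54, a two-sided 95% CI for a single proportion will extend 0.060" when the expected proportion, labelled only as AEs, is 0.0543.
- SAP 6.3.1 then splits TEAEs by unit of analysis. For non-ocular events: "The following tables will be created for non-ocular TEAEs (subject-level summary". For ocular events: "For ocular TEAEs, the following data will be summarized (eye-level summary", with "the frequency (number and percentage), and the corresponding 95% CI of eyes with" each category of event.
- SAP 13 lists one overall AE table for each class: Table 14.3.1.1 for non-ocular events, and "Table 14.3.1.3: Overall Summary of Ocular Treatment-Emergent Adverse Events (TEAEs) FAS". It lists no overall table for the two classes together and none for subjects with an ocular event.
- SAP 3.1 sets the interval method: "For proportions, 95% CIs will be calculated using the exact Binomial (Clopper-Pearson) method".
- Both eyes of every subject are exposed. After Day 1, "subjects will be asked to self-administer 1-2 drops in each eye; four times a day".
- BCVA in SAP 6.3.2 is also summarised by eye: "The mean BCVA score will be presented together with the corresponding 95% CI".

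Neither document mentions correlation between the eyes of one subject.

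**The concern.** There are two separate problems.

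**The missing rate.** AEs are a named safety endpoint, and the one proportion the study was sized to estimate is a proportion of subjects with AEs. No planned table estimates such a proportion across all TEAEs, or for ocular TEAEs alone. The gap falls on the most relevant events, since most of the known risks in Protocol 9.7.1 are ocular. The eye denominator is even applied to subject-level outcomes such as death.

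**The intervals.** Clopper-Pearson assumes independent units. Two eyes of one person receiving the same product may well respond alike. If they do, counting each eye as an independent observation overstates the information and gives intervals that are too narrow. The same applies, less importantly, to the CI of the mean BCVA at each visit.

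**Working it through.** **1. Reproduce the planning figure.** Inputs from SAP 8: p = 0.0543, n = 54, two-sided 95%, normal approximation.

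- Subjects: 1.96 × √(0.0543 × 0.9457 / 54) = 0.0604, stated as 0.060.
- Eyes: 1.96 × √(0.0543 × 0.9457 / 108) = 0.0427.

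The entries of SAP Table 3 (5.81%, 8.00%, 11.55%, 13.34%) also reproduce with n = 54. The planning unit is the subject.

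**2. Can the planned tables yield a subject-level rate?** The ocular table counts eyes, so it does not show whether two affected eyes belong to one person. The two overall tables cannot be added, because neither shows which subjects had both kinds of event. Suppose 6 of 108 eyes are affected:

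| Distribution | Subjects | Rate | Clopper-Pearson 95% CI |
|---|---|---|---|
| All bilateral | 3/54 | 5.6% | 1.2% to 15.4% |
| All unilateral | 6/54 | 11.1% | 4.2% to 22.6% |
| As planned (eyes) | 6/108 | 5.6% | 2.1% to 11.7% |

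This twofold range needs no assumption about correlation.

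With an assumed between-eye correlation ρ, the expected proportion of subjects with at least one affected eye is 2p − [p² + ρp(1 − p)]. At an eye rate p = 0.0543, p² = 0.0029 and p(1 − p) = 0.0514. The result is 10.6% at ρ = 0, 8.0% at ρ = 0.5 and 5.4% at ρ = 1.

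**3. Coverage of the eye-level interval.** Each subject contributes 0, 1 or 2 affected eyes, with P(2) = p² + ρp(1 − p) and P(1) = 2p(1 − p)(1 − ρ). Convolving this over N subjects gives the exact distribution of the eye count. Coverage is the total probability of counts whose Clopper-Pearson interval on 2N eyes contains p. With p = 0.0543, and N = 54 (evaluable) or 68 (recruited, the largest possible FAS):

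| ρ (assumed) | N = 54 | N = 68 |
|---|---|---|
| 0 | 96.8% | 96.4% |
| 0.25 | 94.5% | 93.9% |
| 0.5 | 91.8% | 91.1% |
| 0.8 | 89.0% | 87.4% |
| 1 | 87.9% | 81.4% |

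Coverage at a single rate moves up and down because counts are discrete. Averaged over eye rates from 2% to 10%, it is about 93% (N = 54) and 92% (N = 68) at ρ = 0.5, and about 87% at ρ = 1.

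**4. Zero events.** The upper 95% limit is 6.6% for 0/54 subjects but 3.4% for 0/108 eyes. In the aqueous-deficient group (12 subjects in the Protocol synopsis) it is 26.5% for 0/12 and 14.2% for 0/24. Counting eyes roughly halves the reported bound without adding a subject.

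**5. BCVA visit mean.** With two eyes per subject the variance of the mean is inflated by 1 + ICC, so the naive interval covers 2Φ(1.96/√(1 + ICC)) − 1. This is about 92%, 89% and 86% at assumed ICC values of 0.25, 0.5 and 0.8.

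**The case against.** The strongest reply is that little depends on these intervals. SAP 6.2 disclaims inference on safety endpoints, and there is no hypothesis or performance threshold. The listings cover all TEAEs with ocular ones flagged. At about 5% of 54 to 68 subjects, only three or four would be affected, and they could be counted by hand. Eye-level reporting is reasonable for a drop given to each eye, and the Protocol allows summaries of subjects or eyes. The documents also do not say which AEs 0.0543 refers to, and they tabulate precision for other generic rates.

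These points limit the harm but do not fill the gap: a hand count from a listing is not a pre-specified rate with a CI.

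Three technical objections bear on the intervals.

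- **Rate used.** If 5.43% is the subject-level ocular rate, the eye rate is lower: about 2.8%, 3.2% and 3.7% at ρ = 0, 0.25 and 0.5. Coverage for 54 / 68 subjects is then 99.0% / 96.4%, 96.5% / 95.6% and 90.8% / 94.5%. So there is no shortfall at ρ = 0.25, and at 0.5 it depends on N. At ρ of 0.8 to 1 it persists, with coverage of about 81% to 91%.
- **Discreteness.** At ρ = 1 and 68 subjects, coverage is 81.4% at an eye rate of 5.43% but 91.6% at 5.0%. Single values should not be over-read; the averages in step 3 show that the tendency remains.
- **Table shells.** They are a separate document and were not available. If they show right and left eyes in separate columns, each CI rests on one eye per subject and the pairing point falls away. Pooling is the natural reading of the SAP text. The missing subject-level rate stands either way.

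**Conclusion.** The concern holds and should be fixed.

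The missing rate follows from the SAP text and table list alone. No planned summary gives the proportion of subjects with an ocular TEAE or with any TEAE, although the endpoint-specific sizing figure is for AEs in subjects. The same eye-level result can stand for subject rates that differ by a factor of two.

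The interval point holds on the reading that both eyes are pooled, and its size depends on a correlation the documents do not give. Undercoverage is negligible at ρ of about 0.25 or less, a few percentage points on average at 0.5, and clear at high correlation. The consequence is overstated precision in a descriptive report, not a wrong decision. For BCVA only the CI of the visit mean is affected, and that is secondary.

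**What to change.** In SAP 6.3.1, with a matching entry in SAP 13, add text such as: *The number and percentage of FAS subjects with any TEAE, and with any ocular TEAE in at least one eye, each also for device-related and for serious events, will be presented with Clopper-Pearson 95% CIs, overall and by DED group.*

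Keep the eye-level ocular counts, but show them without CIs or with CIs adjusted for clustering within subject.

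As a secondary change, in SAP 6.3.2 keep the eye-level BCVA summary and compute the CI of the mean with a standard error clustered on subject.

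The cost is SAP wording, one table entry and a few table rows. No new data are needed. The AE table becomes slightly longer and the intervals wider.

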#### 7.3.4.4 Device Deficiencies

Device deficiencies will be collected at the time points specified in Table 4.

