## Device Deficiencies

A device deficiency is an inadequacy of a medical device with respect to its identity, quality, durability, reliability, safety, or performance. A device deficiency may or may not be associated with patient harm (i.e., ADE or SADE); however, not all ADEs or SADEs are due to a device deficiency. The Investigator should determine the applicable category listed in the Device Deficiency eCRF for the identified or suspect device deficiency and report any patient harm separately. Examples of device deficiencies include the following:

- Failure to meet product specifications
- Unsealed device packaging
- Suspected product contamination

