#### 9.3 Procedures for Recording and Reporting

AEs are collected from the time of informed consent completion and throughout the duration of the study. Any preexisting medical conditions or signs/symptoms present in a subject prior to obtaining informed consent are not considered AEs in the study and should be recorded in the Medical History section of the eCRF.

For each recorded event, the ADEs and SAEs documentation must include: date of occurrence, severity, treatment (if applicable), outcome, and assessments of the seriousness and causality. In addition, the Investigator must document all device deficiencies reported or observed with the study device on the Device Deficiency eCRF. The site must submit all available information on ADEs, SAEs, and device deficiencies to the study Sponsor immediately as follows:

- All SAEs must be reported immediately (within 24 hours) of the Investigator or site's awareness.
- ADEs that do not meet seriousness criteria and device deficiencies must be reported within 10 calendar days of the Investigator or site's awareness.
- A printed copy of the completed SAE and ADE and/or Device Deficiency eCRF must be included with product returns.
- Additional relevant information after initial reporting must be entered into the eCRF as soon as the data become available.
- Any changes to concomitant medications must be documented on the appropriate eCRFs.
- All relevant information from Discharge Summary, Autopsy Report, Certificate of Death etc., if applicable, must be documented in the narrative section of the SAE and ADE eCRF.

*Note:* Should the EDC system become non-operational, the site must notify the Sponsor designee (ICON Clinical Research SAE Hotline) at [contact]. The reported information must be entered into the EDC system once it becomes operational.

Study Sponsor representatives may be contacted for any protocol-related question and their contact information is provided in the Project Team Contact List included in the Investigator Site File.

Further, depending upon the nature of the AE or device deficiency being reported, the Study Sponsor (or designee) may request copies of applicable portions of the subject's medical records. The Investigator must also report all AEs and device deficiencies that could have led to a SADE according to the requirements of regulatory authorities or IRB/IEC.

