#### 2.1. Full Analysis Set (FAS)

The FAS will include all subjects/eyes exposed to at least one dose of Systane Complete PF. The FAS will be the primary analysis set for all effectiveness and safety analyses.

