- Listing 16.2.6.2.1: Listing of Biomicroscopy Findings FAS
- Listing 16.2.6.2.2: Listing of Corneal Staining Findings FAS
- Listing 16.2.6.3.1: Listing of Device Deficiencies FAS
- Listing 16.2.6.4.1: Listing of Pregnancy FAS

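### Adverse events and device deficiencies are collected before dosing, but the SAP gives no event-level output for those in consented subjects who are never dosed

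*SAP*

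**What the plan says.** **Collection.** Protocol 9.3 states that "AEs are collected from the time of informed consent completion and throughout the duration of the study", and SAP 6.3.1 agrees: "All AEs will be collected from the time of signed IC until study participation is complete". For deficiencies, Protocol 7.3.4.4 says "Device deficiencies will be collected at the time points specified in Table 4", and that table marks both rows at Visit 1, the combined screening and baseline visit. An eCRF is completed for every enrolled subject (Protocol 10.3), and SAP 3.3 defines enrolled as having signed consent.

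**Reporting.** SAP 2.1 says "The FAS will include all subjects/eyes exposed to at least one dose of Systane Complete PF". The only other set, the per-protocol set, is a subset of it (SAP 2.2). SAP 6.3 puts all safety analyses on the FAS. SAP 6.3.1 bases adverse event analyses on treatment-emergent events unless it says otherwise, and it nowhere says otherwise; on listings it adds "Supportive listings will be provided for all TEAEs". The matching entries in SAP 13 are "Listing 16.2.5.1: Listing of Treatment-Emergent Adverse Events (TEAEs) FAS" and "Listing 16.2.6.3.1: Listing of Device Deficiencies FAS". The deficiency summary, Table 14.3.4.1, carries the same FAS label.

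**Undosed subjects are foreseen.** SAP 3.3 gives non-treated subjects their own baseline rule, SAP 4.1 counts non-eligible enrolled subjects, and Protocol Table 4 allows an exit form at Visit 1.

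**The concern.** The reporting filter is exposure to the drops, but two of the event types being collected do not depend on exposure.

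- **Test-procedure events.** The eCRF asks separately about relationship to test procedure (SAP 6.3.1). The Visit 1 procedures include slit-lamp examination with fluorescein staining, and a subject can undergo them without ever being dosed.
- **Device deficiencies.** These are a named safety endpoint. The protocol's own examples include "Unsealed device packaging" and suspected contamination, either of which could be noticed before the first drop. A deficiency that leads to no dose being given would remove the subject from the set meant to report it.

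At stake is the completeness of a descriptive safety report: an event collected under the protocol, possibly a serious one, could be in the database with its details shown nowhere in the planned outputs.

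**Working it through.** **1. The plan's own safety figure.** SAP 8 gives a 95% half-width of 0.060 for an adverse event proportion of 0.0543 with n = 54. The Wald formula gives 1.96 × √(0.0543 × 0.9457 / 54) = 0.0604, which agrees. The tabulated precisions of 5.81%, 8.00%, 11.55% and 13.34% for rates of 5%, 10%, 25% and 50% also reproduce. None of these is affected by this point.

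**2. Trace of each output in SAP 13.**

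| Output | Number | Event filter | Population |
|---|---|---|---|
| Adverse event tables (14.3.1.1 to 14.3.1.4.3) | 8 | Treatment-emergent | FAS |
| Adverse event listing (16.2.5.1) | 1 | Treatment-emergent | FAS |
| Deficiency table (14.3.4.1) | 1 | None | FAS |
| Deficiency listing (16.2.6.3.1) | 1 | None | FAS |

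The total is 8 + 1 + 1 + 1 = 11. A subject who is never dosed is outside the FAS, so an event in that subject appears in 0 of the 11.

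**3. Whether another rule rescues the event.**

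- SAP 6.3.1 and 12.1 treat an event with a wholly missing onset date as treatment-emergent. That does not bring an undosed subject into the FAS.
- SAP 3.1 makes a general promise to list relevant subject data. The specific listing titles are narrower.
- SAP 6.3.4 says the number of deficiencies reported over the study will be tabulated, with no dosing condition. It sits under SAP 6.3, which sets the FAS, and the table title says FAS. These statements need reconciling.
- The disposition table starts from enrolled subjects, and Listing 16.2.1.1 has no FAS label. Protocol 6.4.6 includes adverse event and technical device problem among the exit reasons, so a reason could appear there. Event term, severity, seriousness, relatedness and deficiency type are not planned there.

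**4. Who is not affected.**

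- Treatment emergence is judged by date, not time. A procedure-related event on Day 1 before the first drop counts as treatment-emergent if the subject is dosed that day.
- A subject dosed from a replacement unit after a defect was found is in the FAS, and so is the deficiency.

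**5. Illustrative size (both inputs assumed).** The documents give neither the number undosed (m) nor the event rate in such subjects (r). The chance of at least one event without event-level output is 1 − (1 − r)^m:

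| Undosed m | r = 0.5% | r = 1% | r = 2% | r = 5.43% |
|---|---|---|---|---|
| 1 | 0.5% | 1.0% | 2.0% | 5.4% |
| 3 | 1.5% | 3.0% | 5.9% | 15.4% |
| 5 | 2.5% | 4.9% | 9.6% | 24.4% |

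The last column uses the planning rate for the study and is probably too high for a single pre-dose visit.

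**The case against.** The strongest defence has five parts.

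- **Exposed-only safety summaries are deliberate and consistent.** Protocol 8.1 makes the FAS the primary set for safety, and the SAP follows it. This stands for the tables. It does not bar a listing on enrolled subjects.
- **Few subjects are exposed to the gap.** The symptom questionnaire precedes every other test and is scored for eligibility (Protocol 7.3.3.1), and no eligibility criterion rests on a staining or slit-lamp result. Many screen failures may leave before any such procedure. This stands and limits the size.
- **The deficiency scenario is narrow.** It needs a defect found before the first drop and a subject who is then never dosed. Nothing in the documents says that a defective unit ends participation. This also stands.
- **Oversight is intact.** Protocol 9.3 requires serious events to reach the sponsor within 24 hours, and deficiencies and non-serious device effects within 10 days, with no FAS condition. A reader might infer that safety surveillance is weakened; the documents do not support that. The gap is in the planned analysis outputs.
- **The table shells are a separate document** and might be broader. The titles in SAP 13 nevertheless say FAS.

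A reader might also infer that these events vanish from every planned output. That goes too far, because the disposition outputs could show an exit reason.

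**Conclusion.** The gap is real but minor. Events in consented, never-dosed subjects have no event-level output, and the FAS label on the deficiency outputs does not match SAP 6.3.4. The number of events involved is not stated and is probably very small. This assumes, as the schedule shows, that consent, screening and first dose fall on one day.

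Two stronger quantitative readings are not supported. First, 0.0543 × 54 = 2.9, so a reader might treat one omitted event as about a third of those expected. That mixes populations: 54 is the evaluable target, and an event in an undosed subject would not belong in that numerator. Second, a reader might take 68 − 54 = 14 as a guide to the number undosed. The protocol's overview describes the 54 as subjects completing treatment, so the difference must also cover dropout after dosing, and the documents give no undosed count.

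The point concerns completeness of safety reporting. It does not touch the primary endpoint, the sample size or any FAS percentage.

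**What to change.** 1. Change Listing 16.2.5.1, and the matching sentence in SAP 6.3.1, to all adverse events in all enrolled (consented) subjects, with flags for treatment-emergent, serious, ocular, procedure-related and undosed.
2. Run Listing 16.2.6.3.1 on all enrolled subjects.
3. Reconcile Table 14.3.4.1 with SAP 6.3.4 by keeping its FAS results and adding an overall-only count, or a footnote, for deficiencies in undosed subjects.
4. Keep all treatment-emergent tables on the FAS, in line with Protocol 8.1.

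The cost is a small SAP edit, a changed population filter on two listings and one added count or footnote. No new data are needed, and the enrolled population is already defined in SAP 3.3. Undosed subjects may have no dry eye disease group, so they should be shown overall only, as SAP 4.1 already does for enrolled and non-eligible counts.
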